Full venographic assessment must include the femoral vein, iliac veins, renal veins, and IVC at the index procedure, for any reinterventions, and if the 12-month site reported or core lab adjudicated DUS shows >50% stenosis or occlusion of the stented segment. In addition, venography may be required for the 24 or 36-month DUS shows >50% stenosis or occlusion of the stented segment **and** the subject is symptomatic requiring a reintervention. Operators will be trained on the venography protocol provided by the core laboratory. No test cases are required for venography.

A comprehensive overview for abdominal venography acquisition requirements can be found in the core laboratory manual.

9.7. **Duplex Ultrasound Assessment**

Abdominal/pelvic venous DUS is accepted as an effective method for diagnosis and follow up of iliofemoral obstruction syndrome and DVT. DUS combines spectral Doppler technology in addition to B-mode imaging to allow visualization of blood flow pattern abnormalities within the Iliofemoral veins in the presence of DVT or obstruction. Increased velocities associated with lumen narrowing can be visualized with spectral and color Doppler. B-mode cross-sectional and longitudinal imaging of diameters can also assess obstruction and extrinsic compression. A lack of color fill and B-mode visualization of thrombus can indicate DVT.

B-Mode, Color Doppler, and Spectral Doppler are required at the target vessels: IVC, CIV, EIV, and CFV. Color and Spectral Doppler B-Mode diameters are required at the narrowest point (lesion) of the target vessel and at a normal reference level taken caudal to the lesion. Velocity measurements are required at the narrowest point (lesion) of the target vessel and at a normal reference level taken caudal to the lesion.

Abdominal Venous DUS is required at the 30-day, 6-month, 12-month, 24-month, and 36-month follow up visits. Operators will be trained on the DUS protocol provided by the core laboratory. Each site is required to submit a test DUS exam to the core laboratory prior to performing any study related DUS exams.

A comprehensive overview for DUS acquisition requirements can be found in the core laboratory manual.

9.8. **X-ray Assessment**

An X-ray assessment will be performed at the 12-month, 24-month, and 36-month follow-up visits to assess the DUO Stent(s)' implant integrity for all subjects in whom at least one DUO Stent was placed during the index procedure.

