15. REQUIRED FOLLOW-UP VISITS AND ASSESSMENTS

All subjects will be required to return for clinic follow-up visits as outlined in **Section 8.1** and in the sections below.

In the event of a public health crisis, a global pandemic, a natural disaster, or any other event which would preclude research sites from conducting research or restrict subjects' ability to attend follow-up visits, guidance will be provided by the Sponsor regarding visit windows.

15.1. 30-day Follow-up Visit (-2 days / +14 days post-Index Procedure)

The following assessments are required to be performed at the 30-day follow-up visit:

- SARS-CoV-2 Testing (if required per Section 9.2)
- DUS
- Venous Ulcer Assessment
- Adverse event assessment
- Review of concomitant medications

15.2. 6-month Follow-up Visit (±30 days post-Index Procedure)

The following assessments are required to be performed at the 6-month follow-up visit:

- SARS-CoV-2 Testing (if required per Section 9.2)
- Venous Ulcer Assessment
- CEAP Classification
- Villalta Score
- VCSS Pain Score
- DUS
- VEINES-QOL/Sym Questionnaire
- EQ-5D-3L Questionnaire
- Adverse event assessment
- Review of concomitant medications

15.3. 12-month Follow-up Visit (±30 days post-Index Procedure)

The following assessments are required to be performed at the 12-month follow-up visit:

- SARS-CoV-2 Testing (if required per Section 9.2)
- Venous Ulcer Assessment
- CEAP Classification

- Villalta Score
- VCSS Pain Score
- DUS
- X-ray of implanted stent(s)
- VEINES-QOL/Sym Questionnaire
- EQ-5D-3L Questionnaire
- Adverse event assessment
- Review of concomitant medications
- Follow-up venogram and IVUS are required if DUS suggests >50% stenosis or occlusion of the stented segment, or if the DUS is non-diagnostic or sub-optimal (i.e., due to obesity). If a follow-up venogram/IVUS is refused by the subject, this must be documented and will not be considered a protocol deviation and the DUS will be used if available.

15.4. **24-month Follow-up Visit (\pm 30 days post-Index Procedure)**

The following assessments are required to be performed at the 24-month follow-up visit:

- SARS-CoV-2 Testing (if required per Section 9.2)
- DUS
- X-ray of implanted stent(s)
- Venous Ulcer Assessment
- CEAP Classification
- Villalta Score
- VCSS Pain Score
- VEINES-QOL/Sym Questionnaire
- EQ-5D-3L Questionnaire
- Adverse event assessment
- Review of concomitant medications

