19.2. Analysis Groups

A subject is defined as ITT and officially enrolled in the study once the DUO Venous Stent System is advanced through the introducer sheath.

Subjects in whom no DUO Stent implant is placed will be exited after 30 days. Subjects in whom at least one DUO Stent implant is placed will be followed for 36 months.

The full analysis set (FAS) are subjects who meet the ITT definition and have data evaluable for the primary endpoints.

The PP population will be defined as ITT subjects with evaluable data that have met the definition for device success, excluding subjects meeting criteria for a protocol violation(s) as outlined in **Section 17.8** and as determined by the Sponsor.

In addition, a SARS-CoV-2 positive population will be defined as:

1. Any documented confirmation of a SARS-CoV-2 positive test result or SARS-CoV-2 positive antibody test (at any approved testing site) from screening through study exit. Subjects will be grouped according to when they became SARS-CoV-2 positive based on the date that testing was performed as compared to the index procedure (i.e., within 30 days, greater than 30 days but within 12 months, greater than 12 months).
2. In the absence of a SARS-CoV-2 test, subjects will be required to complete a COVID-19 questionnaire. Any subject that completes a questionnaire after screening and answers YES to any question on the questionnaire will be included in the SARS-CoV-2 positive population.
3. Regardless of SARS-CoV-2 status or COVID-19 questionnaire results, all adverse events will be assessed by the PI for relatedness to a possible COVID-19 infection by indicating YES, NO, or UNKNOWN.

Any subject that has an adverse event where the PI indicates YES for relatedness will be included in the SARS-CoV-2 positive group.

Due to the unknown but possible risks associated with COVID-19 and hypercoagulability, once a subject is placed in the SARS-CoV-2 positive population, they will remain there regardless of future SARS-CoV-2 test results and or vaccination status. Any subject not meeting the above criteria will be placed in the SARS-CoV-2 Negative population.

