19.7. Handling of Missing Data

A sensitivity analysis to the missing data in the ITT sample will be conducted for both the primary safety and efficacy endpoints in the SARS-CoV-2 negative subset and all subjects. The sensitivity analysis will include a best case, worst case and tipping point analysis. The best-case analysis will impute successes for the missing data. The worst-case analysis will impute failures for missing data. The tipping point analysis starts with the best-case analysis and continues until the worst-case analysis is completed, by increasing the number of missing cases imputed as failures by one in each analysis. The goal of the tipping point analysis is to determine at what point the imputation of

failures causes the statistical evaluation of the endpoint to lose statistical significance. If the worst-case analysis maintains statistical significance, the tipping point analysis is not necessary.

19.8. **Summary of Baseline Demographics, Index Procedure Measurements, and Subject Compliance**

Baseline demographics including at a minimum gender, age, and selected medical history will be summarized for ITT subjects overall and in the SARS-CoV-2 – negative subset for primary safety and for primary efficacy. In addition, angiographic characteristics and measurements, as well as procedure characteristics will be summarized.

Subject follow-up and compliance with the protocol will be reported. The number and percent of subjects enrolled, completing study-required follow-ups, and completing the study will be summarized. The subjects who exit the study early will be summarized along with the reason for early study termination.

19.9. **COVID-19 Statistical Considerations**

Given that COVID-19 has been associated with a hypercoagulable state which has the potential to increase MAE occurrence and decrease patency, the study has been modified to test the primary safety and effectiveness hypotheses in both the SARS-CoV-2 negative subset and all subjects (regardless of SARS-CoV-2 status).

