19.11. Primary Efficacy Objective

Subjects Included the Analysis: Subjects who meet the ITT definition.

Efficacy: Primary patency of stented segment (confirmed by core laboratory) at 12 months evaluated per subject.

Hypothesis:

H_0 : Proportion of subjects with primary patency (p_{p_pat}) is less than or equal to performance goal (PG) at 12 months, $p_{p_pat} \leq PG$

H_1 : Proportion of subjects with primary patency is greater than the performance goal at 12 months, $p_{p_pat} > PG$

The primary patency proportion will be calculated such that the numerator is the number of subjects found to be patent at 12 months. The denominator is the total number of subjects found to be patent or not patent at 12 months.

Patency is:

- An in-window patent stenosis assessment with no reintervention per definition prior to the close of the 12-month window.
- In the absence of an in-window stenosis assessment, a subsequent patent stenosis assessment with no prior reintervention per definition can be used to declare patency at 12 months.

Lack of patency is:

- A reintervention per definition prior to the close of the 12-month visit window.
- A non-patent stenosis assessment within the 12-month visit window.

Performance Goal: The PG for primary efficacy will be set when all enrolled subjects complete the index procedure of this pivotal IDE trial based upon the proportions of ITT subjects in each of the disease states, i.e. nonthrombotic (p_{NT_ENROLL}), acute thrombotic (p_{AT_ENROLL}) and chronic postthrombotic (p_{CPT_ENROLL}). The disease state specific PGs were adopted as suggested in Razavi et al¹ that is, the lower 95% confidence limit minus 0.10. The disease state PGs are .83, .70 and .66 for nonthrombotic, acute thrombotic and chronic postthrombotic subjects respectively. The PG for the

pivotal study will be a weighted combination of these disease state specific PGs, where the weights are the proportion of subjects in each disease state in the ITT sample, i.e. study PG = $(p_{NT_ENROLL}) * 0.83 + (p_{AT_ENROLL}) * .70 + (p_{CPT_ENROLL}) * 0.66$. The same PG will be used overall and in the SARS-CoV-2 negative subgroup. In order to have a minimum number of subjects from each disease condition in the ITT sample, the study will require that at least 20% of the ITT subjects are in each of the disease state.

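### Section 19.11 ignores a non-patent scan before the 12-month window, so an untreated early occlusion without an in-window scan leaves the primary patency analysis, or counts as patent if a later scan is patent

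*Combined protocol and SAP*

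**What the plan says.** Section 19.11 defines lack of patency by two routes. The first is "A reintervention per definition prior to the close of the 12-month visit window". The second is "A non-patent stenosis assessment within the 12-month visit window". The window is set in Section 15.3: "12-month Follow-up Visit (±30 days post-Index Procedure").

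Patency also has two routes. One is an in-window patent assessment with no qualifying reintervention. The other applies when there is no in-window assessment: "a subsequent patent stenosis assessment with no prior reintervention per definition can be used to declare patency at 12 months".

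On who is counted, Section 19.11 says: "The denominator is the total number of subjects found to be patent or not patent at 12 months". The primary analysis is run in the full analysis set, which Section 19.2 limits to ITT subjects who "have data evaluable for the primary endpoints".

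Scans before the window are part of the schedule. Section 9.7 states: "Abdominal Venous DUS is required at the 30-day, 6-month, 12-month, 24-month, and 36-month follow up visits". Section 15.6 adds unscheduled scans as clinically indicated, and Section 21.9 sends all of them to a core laboratory.

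On missing data, Section 19.7 plans best-case, worst-case and tipping-point analyses. For the first of these: "The best-case analysis will impute successes for the missing data".

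**The concern.** Section 6.1 defines primary patency as freedom from core-laboratory occlusion or stenosis above 50%, and from clinically driven target lesion reintervention. Section 19.11 turns this into a rule under which an adverse scan before the window has no effect unless a qualifying reintervention follows. That reintervention must be a procedure for symptoms with IVUS-confirmed stenosis or occlusion, so an occlusion left untreated never triggers it.

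If the subject then dies, withdraws or misses the 12-month scan, evidence against patency is discarded. If the subject is next scanned after the window and is patent, the second patency bullet makes the subject a success. The affected subjects are selected for a bad finding, so the primary proportion shifts towards exceeding the performance goal. At stake is Type I error control on the primary efficacy claim.

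**Working it through.** **1. Tracing one subject.** Take a subject with a non-patent 6-month core-laboratory DUS, no reintervention and no in-window scan.

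| Analysis | Section | No later patent scan | Later patent scan |
|---|---|---|---|
| Primary patency | 19.11 | Not in the denominator | Patent |
| Kaplan-Meier | 19.11, Additional Analysis | Censored at last follow-up (same in-window limit on the event) | Censored |
| Best case | 19.7 | Success | Not missing, so patent |
| Worst case | 19.7 | Failure | Not missing, so patent |
| Tipping point | 19.7 | Moves from success to failure | Not missing, so patent |

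The safety analysis in Section 19.10 works differently. Its denominator expressly keeps subjects who had an MAE and left before 30 days.

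**2. Inputs (Sections 19.3 and 19.11).** N = 128 evaluable; performance goals 0.83, 0.70 and 0.66 (NT, AT, CPT); assumed patency 0.96, 0.87 and 0.79; Z > 1.96 with variance taken from the performance goals. For equal thirds:

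- PG = (0.83 + 0.70 + 0.66)/3 = 0.73
- v = (0.83×0.17 + 0.70×0.30 + 0.66×0.34)/3 = (0.1411 + 0.2100 + 0.2244)/3 = 0.1918
- Z = (x/n − 0.73)/√(v/n), because weighting by analysis-set proportions reduces to total patent over total evaluable

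**3. The plan's own figure.** Exact power for equal thirds under this rule is 98.5%; the table in 19.11 gives 98%. It reproduces.

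**4. Effect on a given result.** Restore k excluded subjects as failures, keeping the mix at equal thirds. At n = 128 the standard error is √(0.1918/128) = 0.0387. The smallest passing count is 104, since 103/128 gives Z = 1.93.

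| Result as planned | k restored | Rate | Z | Outcome |
|---|---|---|---|---|
| 104/128 | 0 | 81.3% | 2.13 | pass |
| | 1 (104/129) | 80.6% | 1.98 | pass |
| | 2 (104/130) | 80.0% | 1.82 | fail |
| 112/128 | 0 | 87.5% | 3.75 | pass |
| | 8 (112/136) | 82.4% | 2.49 | pass |
| | 12 (112/140) | 80.0% | 1.89 | fail |

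At the 0.2/0.2/0.6 mix the threshold is 100/128, and at 0.6/0.2/0.2 it is 108/128. In both, one restored subject turns the pass into a fail (Z = 1.84).

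**5. Effect on Type I error.** Set true patency, with early failures counted as failures, at the performance goal in each disease state. Expected failures are 128 × 0.27 = 34.6. Remove a fraction d of them from numerator and denominator and apply the plan's Z (simulation, equal thirds, one test at 1.96).

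| d (assumed) | Subjects lost, 34.6 × d | Type I error |
|---|---|---|
| 0 | 0 | 1.9% |
| 5% | 1.7 | about 4% |
| 10% | 3.5 | about 7% |
| 15% | 5.2 | about 11% |

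Nominal is 2.5%. The values of d are assumptions; the documents give no count.

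**The case against.** **An early adverse DUS is not proof of failure.** Section 6.1 asks for IVUS confirmation, and Section 9.5 ties the scheduled-visit IVUS to the 12-month DUS, not to the 30-day or 6-month one. A reader might infer that the plan throws out established failures. The documents do not support that: most early findings would be unconfirmed, and an in-window patent scan would properly override them. This stands, and the fix must address it. It does not justify ignoring the finding. Section 15.3 already lets DUS stand when the 12-month venogram or IVUS is refused.

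**Early patent scans are not carried forward either.** True, but patency at 6 months does not establish patency at 12, whereas an occlusion is the event the endpoint is meant to be free from.

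**The sensitivity analyses would expose the problem.** In part. The worst case counts the excluded subjects as failures, and the best case is only one end of a disclosed range, so a reader should not infer that Section 19.7 hides them. But study success under Section 19.4 rests on the primary test. The worst case also fails every subject whose status is truly unknown, so it cannot isolate this group. None of the three reaches a subject reclassified as patent by a later scan.

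**Safety captures some of these subjects.** New thrombus in the stented segment within 30 days is an MAE. That counts against safety, not efficacy, and does not cover 6-month findings.

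**The group may be very small.** This stands. The 20% attrition allowance covers all causes and includes subjects without an implant, who exit at 30 days. It says nothing about how often this pattern occurs.

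**Conclusion.** The gap is in the current text, and no other section closes it for the primary analysis. It is narrow: the subject needs an adverse scan before the window, no qualifying reintervention and no in-window assessment. For such subjects, exclusion or reclassification as patent can only favour passing, compared with counting them as failures.

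The certainty attaches to the wording, not to the size of the effect. The Type I error of about 4 to 11% assumes that 5 to 15% of true failures are lost in this way, equal thirds, and that the early findings are genuine failures.

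A reader might infer that the trial's efficacy conclusion is unreliable whatever the result. The figures do not support that. At the assumed patency rates power is about 98%, and 112/128 survives eight restored failures. The rule matters in a close result, where one or two subjects decide the outcome. It should be settled before outcomes are analysed.

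**What to change.** 1. In Section 19.11, add a third form of lack of patency: where there is no in-window assessment, a core-laboratory adjudicated occlusion or stenosis above 50% on any scheduled or unscheduled scan before the window. An in-window assessment, where present, still decides.
2. Give the new bullet precedence over the one that accepts a later patent scan, or restrict that bullet to subjects with no earlier non-patent scan. Otherwise one subject could meet both definitions.
3. State that the core-laboratory DUS reading is used when no IVUS was done, and add a sensitivity analysis limited to IVUS-confirmed findings.
4. Make the same change to the Kaplan-Meier event definition, so that the primary and supportive analyses agree.
5. In Section 19.7, state that these subjects are not missing, so the best case never imputes them as successes.

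The cost is wording only. The scans are already scheduled and sent to the core laboratory, and no visit or procedure is added. Observed patency may be slightly lower, and some early DUS findings counted as failures will lack IVUS confirmation; the analysis in item 3 shows how much that matters.

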Sample Size Rationale: With an expected FAS sample size of N=128, one-sided Type I error less than or equal to 2.5%, and assumed primary patency at 12 months equal to .96, .87, .79, i.e. the point estimates for primary patency from Razavi et al for nonthrombotic, acute thrombotic, and chronic postthrombotic respectively, the power for primary efficacy ranges from 96 – 99% depending on proportion in each disease-state given a minimum of at least 20% in each group. The table below provides the matrix of simulated power varying the ITT proportions for the disease states.

Power Calculations Using Simulation for the Primary Statistical Analysis

Proportion of Subjects Expected in Each Group			Assumed Freedom from Primary Efficacy				Calculated Performance Goal				Power at N=128 Evaluable (20% attrition for N=160 enrolled)
NT	AT	CPT	NT	AT	CPT	Pooled	NT	AT	CPT	PG	One-sided Type I error = 2.5%
0.3333	0.3333	0.3333	0.96	0.87	0.79	0.873	0.83	0.7	0.66	0.73	98%
0.2	0.2	0.6	0.96	0.87	0.79	0.84	0.83	0.7	0.66	0.702	96%
0.2	0.6	0.2	0.96	0.87	0.79	0.872	0.83	0.7	0.66	0.718	99%
0.6	0.2	0.2	0.96	0.87	0.79	0.908	0.83	0.7	0.66	0.77	96%
0.3	0.3	0.4	0.96	0.87	0.79	0.865	0.83	0.7	0.66	0.723	97%
0.3	0.4	0.3	0.96	0.87	0.79	0.873	0.83	0.7	0.66	0.727	99%
0.4	0.3	0.3	0.96	0.87	0.79	0.882	0.83	0.7	0.66	0.74	98%
0.4	0.4	0.2	0.96	0.87	0.79	0.89	0.83	0.7	0.66	0.744	99%
0.4	0.2	0.4	0.96	0.87	0.79	0.874	0.83	0.7	0.66	0.736	98%
0.2	0.4	0.4	0.96	0.87	0.79	0.856	0.83	0.7	0.66	0.71	98%

Primary Statistical Analysis: The primary statistical analysis will be conducted in the FAS subjects overall and in the SARS-CoV-2 negative subgroup. The primary statistical comparison will use a one-sample Z-test comparing the proportion of subjects with primary patency to the PG using a one-sided $\alpha = 0.025$ equivalent to a z-score of 1.96. The variation in the proportion will be estimated using the disease-specific performance goals themselves, i.e. under the null, rather than use the estimated patency rates, i.e. under the alternative.

The estimates that will be observed for primary patency in each disease etiology are noted as follows:

$\hat{p}_{p_pat_NT}$ = The primary patency observed in the NT subjects.
 $\hat{p}_{p_pat_AT}$ = The primary patency observed in the AT subjects.
 $\hat{p}_{p_pat_CPT}$ = The primary patency observed in the CPT subjects.

The percent of subjects in the FAS with each disease etiology are noted as follows:

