p_{NT_FAS} = The proportion of FAS subjects with NT disease etiology.
 p_{AT_FAS} = The proportion of FAS subjects with AT disease etiology.
 p_{CPT_FAS} = The proportion of FAS subjects with CPT disease etiology.

The number of subjects in the FAS set with each disease etiology are noted as follows:

n_{NT_FAS} = The number of FAS subjects with NT disease etiology.
 n_{AT_FAS} = The number of FAS subjects with AT disease etiology.
 n_{CPT_FAS} = The number of FAS subjects with CPT disease etiology.

The primary patency for the hypothesis test is calculated as:

$$p_{p_pat} = p_{NT_FAS} * \hat{p}_{p_pat_NT} + p_{AT_FAS} * \hat{p}_{p_pat_AT} + p_{CPT_FAS} * \hat{p}_{p_pat_CPT}$$

with the variance of primary patency calculated as follows:

$$\text{var}(p_{p_pat}) = ((p_{NT_FAS})^2 PG_{NT}(1 - PG_{NT}))/ n_{NT_FAS} + ((p_{AT_FAS})^2 PG_{AT}(1 - PG_{AT}))/ n_{AT_FAS} + ((p_{CPT_FAS})^2 PG_{CPT}(1 - PG_{CPT}))/ n_{CPT_FAS}$$

Such that the Z score is calculated as follows:

$$Z = (p_{p_pat} - PG) / \text{square root}(\text{var}(p_{p_pat}))$$

When $Z > 1.96$, the primary patency is found to be significantly greater than the performance goal with two-sided Type I error held at 5%, i.e. two-sided p-value < 0.05 .

The two-sided p-value in the SARS-CoV-2 negative subgroup and all subjects will be calculated and ordered from largest to smallest. If the largest p-value, is statistically significant at $p < 0.05$ then the

hypothesis test is statistically significant in both the SARS-CoV-2 negative subset and all subjects. If not, testing continues to the smallest p-value. If the smallest p-value < 0.025 then the hypothesis test is statistically significant in the group for which the smallest p-value is associated with. If the smallest p-value ≥ 0.025 , then the hypothesis test is not statistically significant in either the SARS-CoV-2 negative subset nor all subjects.

Additional Analysis: As a supportive analysis to the primary patency analysis, a Kaplan-Meier analysis will also be performed using the patency data overall and in the SARS-CoV-2 negative subset. Time 0 is the index procedure and the event is lack of patency based on 1) reintervention per definition 2) a non-patent stenosis assessment within the 12 month visit window. For subjects who do not experience an event, the time of censoring is the date of the last follow-up whether scheduled or unscheduled.

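### The primary efficacy Z-test subtracts an ITT-weighted goal from an FAS-weighted patency rate, so its error rate depends on which disease states are evaluable

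*Combined protocol and SAP*

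**What the plan says.** Section 19.11 combines the three state goals into one study goal, "where the weights are the proportion of subjects in each disease state in the ITT sample". Section 19.5 locks that number when enrolment ends, before any efficacy analysis.

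The test then uses a different set of weights. The observed state patencies are combined with FAS proportions; the NT weight, for instance, is "The proportion of FAS subjects with NT disease etiology". The variance uses the same FAS weights. Section 19.2 defines the set by evaluability: "The full analysis set (FAS) are subjects who meet the ITT definition and have data evaluable for the primary endpoints".

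Two further statements matter. On the variance: "The variation in the proportion will be estimated using the disease-specific performance goals themselves, i.e. under the null". On the COVID analyses: "The same PG will be used overall and in the SARS-CoV-2 negative subgroup". Under section 19.4, efficacy success in either all subjects or the SARS-CoV-2 negative subset is enough, with a Hochberg correction.

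**The concern.** The state goals span 17 points (0.83 to 0.66), so the appropriate combined goal depends on the disease mix of the subjects tested. The locked goal reflects the mix enrolled, while the rate set against it reflects the mix that had 12-month data or, in the subset, also stayed SARS-CoV-2 negative. Subjects without a stent count in the ITT weights but exit at 30 days, and nothing makes the planned 20% attrition equal across states.

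If NT subjects are evaluable more often than CPT subjects, the goal is too low for the mix tested and the one-sided 2.5% can be exceeded. In the reverse case the test is conservative and loses power. The power table in 19.11 uses a single mix on both sides, so the problem does not show there. The missing-data analyses in 19.7 are sensitivity analyses, and 19.9 would revisit the common goal only for the effect of infection on outcomes.

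**Working it through.** **Inputs from the documents.** State goals 0.83/0.70/0.66; assumed patency 0.96/0.87/0.79; 160 enrolled, 128 evaluable; success when Z > 1.96 (19.3, 19.11).

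**Assumptions.** Loss and infection by state are not given. Enrolment is taken as 53/54/53, average loss as 20%, and infection as 20% in each state unless stated. State rates are in the order NT/AT/CPT.

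**1. The plan's own figure.** Applying the 19.11 rule exactly with one mix on both sides gives 97.3% to 99.5% power, against the stated 96–99%. Equal thirds gives 98.3% against 98%. Nine of ten rows agree within 2 points. The 60/20/20 row (stated 96%) comes out at 99.4%; nothing here depends on it.

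**2. The shift.** With each state at its own goal,

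E[numerator of Z] = Σ w_FAS·PG_k − Σ w_ITT·PG_k = Σ (w_FAS − w_ITT)·PG_k.

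This is zero when the mixes match and can take either sign otherwise.

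**3. One case worked through: loss 10/20/30%.**
- Goal with ITT weights: (53×0.83 + 54×0.70 + 53×0.66)/160 = 116.77/160 = 0.7298.
- Expected evaluable counts: 47.7, 43.2 and 37.1, total 128.
- Same state goals in the FAS mix: (47.7×0.83 + 43.2×0.70 + 37.1×0.66)/128 = 94.317/128 = 0.7369.
- Shift: about 0.0070, or 0.70 points.
- SE under the plan's variance, where w²/n = w/N: √[(47.7×0.1411 + 43.2×0.2100 + 37.1×0.2244)/128²] = √(24.13/16384) = 0.0384.
- E[Z] = 0.0070/0.0384 = 0.18. The normal tail beyond 1.96 − 0.18 is about 3.8%; simulation, which respects the discrete counts, gives 3.5%.

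**4. Simulated one-sided error with every state at its own goal.** The Hochberg step is met when both Z exceed 1.96 or the larger exceeds 2.24.

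| Loss NT/AT/CPT | Shift (points) | Per test, all subjects | Family-wise |
|---|---|---|---|
| 20/20/20% | 0 | 2.3% | 1.8–1.9% |
| 15/20/25% | +0.35 | 2.8% | 2.3% |
| 10/20/30% | +0.70 | 3.5% | 2.9% |
| 30/20/10% | −0.70 | 1.4% | 1.1% |

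Varying the common infection rate from 2% to 40% leaves the 10/20/30% family-wise error at 2.9–3.1%. If infection follows the same gradient as loss, and weights are recomputed within the negative subset, family-wise error is 2.5–2.6% at 15/20/25% and 3.6–3.7% at 10/20/30%.

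**5. Outcome rules that change who is evaluable.** Lack of patency includes "A reintervention per definition prior to the close of the 12-month visit window", so some failures count without a 12-month image. If 5% or 10% of failures that would otherwise be missing are captured that way, the 10/20/30% case falls to 3.0% or 2.6% per test and 2.5% or 2.1% family-wise. Dependence on mix remains: at 10% capture, per-test error is 1.1% (30/20/10%), 1.7% (equal loss) and 2.6% (10/20/30%). A second rule works the other way: "a subsequent patent stenosis assessment with no prior reintervention per definition can be used to declare patency at 12 months", while a later non-patent image is not listed as failure. With 5–10% shares for both rules, 10/20/30% gives 3.4% per test and 2.8% family-wise.

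**6. Separate check with fixed counts (54/53/53 enrolled, 128 evaluable).** With 49/40/39 evaluable the shift is +0.70 points and the exact error 2.9%, against 1.7% when the goal is weighted by the mix tested. With 38/45/45 the shift is −0.61 points and the error 1.3%, against 2.3%. If all 32 losses came from AT and CPT, E[Z] would be +0.33; if all came from NT, −0.62.

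**The case against.** The strongest defence is that H0 in 19.11 concerns the pooled proportion against a fixed number. The FAS-weighted sum is algebraically the crude FAS proportion, consistent with "The denominator is the total number of subjects found to be patent or not patent at 12 months". Under that H0, Z is centred for any mix. This is correct. But the plan computes its variance with each state at its own goal, and it weighted the goal by state so that it would represent those goals. Under the pooled reading the goal no longer does so for the subjects tested.

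Second, family-wise error decides the efficacy claim, and it stays within 2.5% with equal loss, at 15/20/25% and at 30/20/10%. With loss alone differing, the case above 2.5% is the threefold gradient, and 10% capture of failures brings that to 2.1%. This stands as a limit on size.

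Third, the 3.6–3.7% figure assumes that weights are recomputed within the negative subset. The text does not say so outright, although it is the natural reading of an analysis conducted in that subset. Keeping whole-FAS weights lowers the figure to 2.9% and leaves the loss-only cases unchanged.

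Fourth, the imputations in 19.7 restore the ITT mix for all subjects. They do, but they are not the primary test and do not restore the whole-trial mix in the negative subset.

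Finally, shifts of 0.35–0.70 points are small beside the 14 points or so between assumed patency and goal (0.873 against 0.73 at equal thirds). True, but that gap describes power if the device performs as hoped; it does not limit error at the goal.

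**Conclusion.** The concern holds. The two sides of the primary efficacy comparison use different weights, and no section reconciles them. Under the state-goal null that the plan uses for its variance, error depends on which states are evaluable: roughly 1.4% to 3.5% per test and 1.1% to 2.9% family-wise over the loss-only patterns examined, before any capture of failures by reintervention. It is higher if infection follows the same gradient as loss.

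The mismatch is certain; its size and direction are not. Every figure rests on assumed state-specific rates, and the effect vanishes if loss and infection are alike across states. It is modest, but worth correcting before analysis.

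**What to change.** Keep the goal locked at the end of enrolment and use its weights on both sides:

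- p = Σ p_k,ENROLL × (observed patency in state k)
- var = Σ p_k,ENROLL² × PG_k(1 − PG_k)/n_k, where n_k is the evaluable count in the set analysed.

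Apply this to all subjects and to the SARS-CoV-2 negative subset. Align the numerator and denominator sentence in 19.11, and report the crude FAS proportion alongside.

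With infection equal by state, error is then 2.2–2.3% per test and 1.8% family-wise across the loss patterns (1.6–1.7% and 1.3% at 10% capture).

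The cost is two formulas and one sentence, with no new data. The primary estimate becomes a rate standardised to the ITT mix. That mix includes subjects without a stent, but the planned goal already counts them. The all-subject SE changes by +1.2% (15/20/25%), +2.5% (10/20/30%) or about −1% (30/20/10%). All-subject power at 10/20/30% is 98.3% instead of 99.4%, the higher figure coming with inflated error; at 30/20/10% it rises from 97.3% to 98.8%. The largest cost is in the negative subset when infection also follows 10/20/30%: SE +6% and subset power 93.8% instead of 98.8%, though power to succeed in either set is 97.2% instead of 99.2%. With both gradients reversed, subset power rises from 89.6% to 96.3%.

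An equally sound alternative is to pre-specify that the fixed state goals are weighted by the mix of the set analysed. That keeps the crude proportion as the estimate, but the combined goal is then not a single number at the end of enrolment.
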